## Research project design document

### Project justification

#### 1. Current status and challenges in prognosis prediction of unresectable liver cancer

Hepatocellular carcinoma (HCC) is the third leading cause of cancer-related deaths worldwide, and the treatment of patients with intermediate and advanced stages is particularly challenging. The burden of liver cancer in China is heavy, accounting for about half of the world's new cases and deaths every year, and about 70% of patients have lost the opportunity for surgery when they are diagnosed. In recent years, transcatheter arterial chemoembolization (TACE) combined with targeted and immunotherapy has become a key treatment modality for unresectable HCC. This strategy exerts dual anti-tumor effects through a synergistic mechanism: TACE induces avascular necrosis and releases high concentrations of chemotherapeutic drugs by local embolization of the tumor-supplying arteries; Immune checkpoint inhibitors such as PD-1/PD-L1 activate systemic anti-tumor immune responses by reversing the immunosuppressive state of the tumor microenvironment. Two phase III randomized controlled trials, EMERALD-1 and LEAP-012, showed that TACE in combination with durvalumab and bevacizumab or pembrolizumab and lenvatinib significantly extended median progression-free survival (PFS) to 15.0 months and 14.6 months, significantly better than 8.2 months and 10.0 months with conventional TACE therapy.

However, there is significant clinical heterogeneity in this combination, with studies showing that only about 30% to 40% of patients achieve a significant response, and nearly 60% of patients fail to achieve substantial survival benefit. This difference in efficacy is closely related to tumor molecular heterogeneity, immune microenvironment characteristics, and host liver function status. Imaging evaluation is the main method of efficacy evaluation, but the widely used clinical efficacy evaluation criteria for solid tumors (RECIST v1.1) are mainly based on tumor diameter changes, which has limitations in evaluating the dynamic efficacy of TACE combined with target-immune therapy. This criterion is a static "time slice" analysis, which is difficult to capture the dynamic evolution of the tumor microenvironment during treatment.

Radiomics and deep learning technologies provide a new way to predict the survival of liver cancer. Radiomics constructs a quantitative prediction model by extracting the texture, morphology and functional characteristics of CT/MRI images through high-throughput. Deep learning models, such as convolutional neural networks (CNNs), use end-to-end learning to mine deep features directly from raw images, avoiding the limitations of artificial feature design. However, existing deep learning models still face three challenges: (1) poor interpretability; (2) Insufficient vertical information integration, mostly relying on single-point data;

(3) The models are mostly constructed based on the baseline status of patients, ignoring the dynamic changes of tumor burden and immune landscape in the treatment cycle, which is difficult to guide treatment adjustment in real time and does not meet the needs of precision medicine. Although the traditional longitudinal prediction model can incorporate dynamic changes, it needs to systematically collect follow-up data for multiple visits. In the real world, patient follow-up is often irregular, and there are medical referrals and referrals in other places, resulting in a large number of missing or uneven longitudinal imaging data, and it is difficult to align the information obtained at different time points and different devices. In addition, such models wait for patients to respond to treatment, which has a prediction lag. The LILAC system (Learning-based Inference of Longitudinal imAge Changes) represents an important breakthrough in this direction, which uses a self-supervised time-series deep learning algorithm to analyze small changes in a series of MRI scans to achieve dynamic monitoring of disease progression. The proof-of-concept study showed that LILAC was significantly superior to the traditional method in the prediction of embryonic development time sequence and geriatric cognitive score. In pediatric glioma studies, the time-series deep learning model improved the F1-score of 1-year recurrence prediction by 58.5% by analyzing serial postoperative MRI images, and the prediction performance increased with the increase of historical scans (plateau after 3-6 scans). However, the clinical translation of longitudinal models faces fundamental difficulties: patients with advanced HCC are often unable to complete the full process of imaging follow-up due to disease progression or adverse reactions, resulting in a lack of high-quality time series data; Data heterogeneity is caused by differences in image acquisition protocols in different centers. Ethics and privacy concerns limit multi-center data sharing. Therefore, there is an urgent need to develop new prediction paradigms that do not rely on real post-treatment images. Breakthroughs in Generative Artificial Intelligence provide a revolutionary solution to this.

The core strength of generative models is their ability to learn the latent distribution of data and generate high-fidelity new samples. This field has achieved technological evolution from generative adversarial networks (GANs), variational autoencoders (VAEs) to diffusion models. In recent years, the proposed diffusion model has demonstrated better image generation quality than the previous model in a number of studies through the iterative process of forward noise addition and reverse noise reconstruction. In medicine, generative models were initially used primarily for data amplification and image synthesis (e.g., to generate images of rare diseases to alleviate sample imbalances), but recent advances have expanded into the areas of treatment response simulation and disease course prediction. Compared with traditional prediction models, generative models have shown unique potential in predicting curative effects: they can capture the spatiotemporal dynamics of tumor growth through the hidden spatial representation learning ability of

diffusion models. Based on this, the model can generate virtual images that simulate the optimal treatment response according to the initial state of the patient's tumor and the characteristics of the treatment plan in the absence of data. This provides clinicians with an intuitive tool for predicting efficacy, which helps to improve the robustness of survival prediction and provides a potential reference for subsequent treatment decisions.

## **2. The entry point and significance of this study**

The entry point of this study is to propose "generative longitudinal prediction": only pre-treatment images are needed to generate high-fidelity post-treatment image predictions, which effectively avoids the clinical dilemma of obtaining real longitudinal follow-up data. This paradigm shift not only solves the problem of longitudinal data scarcity, but also develops a new approach to treatment simulation based on digital twins. Clinicians can intuitively evaluate the possible efficacy of different regimens through the virtual multi-time point images generated by the model before treatment, providing a visual basis for individualized treatment decisions. This study integrates generative AI and dynamic risk models to achieve: 1. From static assessment to dynamic deduction; 2. Survival prediction is moved forward; 3. Individualized optimization of treatment plan. It is expected that we can provide more accurate and individualized treatment decision support for patients with advanced liver cancer without relying on longitudinal data, and ultimately improve the survival prognosis and quality of life.

## Research content

### 1. Research Objectives

**Main objectives:** 1) To construct a generative image model based on preoperative CT/MRI; 2) the treatment response was evaluated in the training cohort based on the virtual image images generated by the model, including: disease control rate (DCR) and objective response rate (ORR), and compared with the best treatment response images after real treatment; 3) predict the prognosis of patients based on real pre-treatment imaging images (CT/MRI/DSA) and virtual post-treatment images, including progression-free survival (PFS) and overall survival (OS);

**Secondary objectives:** 1) Integrate text information such as patient demographic data, laboratory examination data, and image reports/surgical records to achieve cross-modal fusion and further improve the performance of the model; 2) Adopt machine learning methods based on causal inference to realize the recommendation of diagnosis and treatment plans.

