#### (2) Selection of research subjects:

This project is a real-world study, including retrospective training, validation and testing cohorts and prospective testing cohorts, all registries are derived from real cases in clinical practice, and the collected case data should include the following requirements:

1. Unresectable hepatocellular carcinoma confirmed by histopathological diagnosis and/or clinical diagnosis (typical imaging features, clinical manifestations, laboratory tests, etc.) (Annex: Guidelines for the diagnosis and treatment of primary liver cancer (2024 edition));
2. Patients who receive TACE combined with targeted immunotherapy on the basis of the diagnosis of unresectable hepatocellular carcinoma;
3. Liver function grade Child-Pugh A or B;
4. Over 18 years old, regardless of gender;
5. Expected survival time  $\geq$  3 months;
6. ECOG PS score  $\leq 2$ ;

7. Meet the following laboratory examination parameters;

- 1) Hematologic function: absolute neutrophil count  $\geq 1.0 \times 10^9 / \text{L}$ ; Platelet count  $\geq 50 \times 10^9 / \text{L}$ ; hemoglobin  $\geq 90 \text{ g/L}$ ; The international normalized ratio is less than 1.7 or the prothrombin time is prolonged by no more than 4 seconds,
- 2) Liver function: alanine aminotransferase/aspartate aminotransferase does not exceed 5 times the upper limit of normal; total bilirubin  $\leq 210 \text{ micromol/L} [\leq 2.38 \text{ mg/dL}]$ ; Albumin  $\geq 28 \text{ g/L}$ ,
- 3) Renal function: serum creatinine does not exceed 1.5 times the upper limit of normal.

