**(6) Evaluation Indicators:**

**Key research indicators**

In this study, the performance of the prediction model was comprehensively evaluated by the following five types of indicators, and all indicators reported point estimates and 95% confidence intervals (1000 times repeated sampling by the Bootstrap method): 1) discrimination: the C-index (Concordance Index) was used to evaluate the consistency of the model's ranking of individual survival time (two patients were randomly selected to predict the probability that the one with longer survival time would actually survive longer); 2) Time-dependent AUC (time-dependent AUC) was used to evaluate the model's ability to distinguish whether an event occurred or not at a preset time point; 3) calibration, the difference between the predicted probability and the actual outcome and the probability distribution were visualized by calibration plot and density plot, and the mean square error of the Brier Score was calculated. 4) Decision Curve Analysis (DCA) was used to evaluate clinical practicability; 5) The proportion of variation explained by the Nagelkerke R^2 assessment model was used.

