### **3. Research Methodology**

This study is based on a multicenter retrospective cohort including a prospective test cohort to include patients with unresectable hepatocellular carcinoma who have received TACE in combination with target-immune therapy. The data comes from the clinical diagnosis and treatment records of 8 tertiary hospitals from 2016 to 2025, and strictly follows the preset inclusion standards.

Generative model construction: diffusion model-based treatment response simulator: input data: enhanced CT/MRI images at the patient's baseline, real post-treatment enhanced CT/MRI images and clinical features (Child-Pugh score, AFP level, treatment plan, etc.). Model architecture: The conditional diffusion model was used to dynamically simulate the virtual follow-up images of the best response after treatment with the treatment protocol (TACE embolic agent dose + target immune drug combination) as the generation conditions. Training mechanism: The model is optimized by comparing the differences in deep visual features between the generated images and the real follow-up images to ensure that the generated results conform to the laws of biological evolution. Quantitatively evaluate the visual fidelity of the generated images (FID index <25); The clinical rationality was scored by 3 interventional radiology experts by blind (on a 5-point scale  $\geq$  4 points were considered qualified).

Dynamic survival prediction framework: Capture 256-dimensional semantic feature vectors from the generated virtual images to characterize the dynamic changes of tumor microenvironment. The depth features extracted by the generative model are fused with the patient's clinical variables, and the key predictors are automatically identified through the gated attention mechanism. Survival risk modeling: Construct a Transformer-based time-series survival model to output individualized survival curves and survival probability predictions at key time points (12/24/36 months).

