Treatment decision support systems: causal effects deduction: quantifying the expected survival benefit of different treatment regimens (eg, TACE + lenvatinib + pembrolizumab versus TACE + bevacizumab + atezolizumab) using a counterfactual analysis framework. Generate a heat map of treatment regimen comparisons to visualize simulated tumor regression differences. Decision rule: When the median survival benefit of a regimen is expected to be more than 3 months and the confidence probability is greater than 80%, the system preferentially recommends the regimen.

Model validation strategy: Stratified by study center, randomly assigned to the training set (70%), validation set (30%), and multiple test sets.

Survival prediction assessment: main indicators: C-index evaluation of overall survival prediction

accuracy; Secondary indicators: 12/24/36 months of time dependence on AUC to assess discriminant ability at a specific time point; Calibration analysis: The Brier score quantifies the prediction error, and the calibration curve evaluates the risk prediction consistency. Comparative experimental design: baseline model (clinical variables only); benchmark model + real follow-up images; Datum model + generate model virtual image.

Reproducibility & Ethics: The model code and preprocessing process are published in the public repository (GitHub). The self-service resampling method (1000 times) was used to calculate the 95% confidence interval.

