## **6. Research plan and forecast progress**

2025/6-2025/12: Complete the collection, cleaning, and statistical analysis of patients' baseline images, efficacy evaluation, and safety data;

2026/01-2026/06: Complete the construction of the generative model, and evaluate and predict the performance of the model;

2025/06-2026/12: Write a research paper and submit it, and complete the final report.

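### Main objective 2 places the virtual-versus-real ORR/DCR comparison in the training cohort, so it measures apparent performance and not prediction in new patients

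*Protocol*

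**What the plan says.** In the Protocol, Research Objectives, main objective 2 states that "the treatment response was evaluated in the training cohort based on the virtual image images generated by the model". The measures are DCR and ORR, and the comparator is the real images of best response after treatment.

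Section 3, Research Methodology, describes how the generator is built. Its input data include "real post-treatment enhanced CT/MRI images and clinical features", alongside the baseline images. On training it says: "The model is optimized by comparing the differences in deep visual features between the generated images and the real follow-up images".

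The purpose is set out in section 2, on the entry point and significance of the study: "only pre-treatment images are needed to generate high-fidelity post-treatment image predictions".

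Item (2), Selection of research subjects, describes the project as "including retrospective training, validation and testing cohorts and prospective testing cohorts". The model validation strategy in section 3 has patients "randomly assigned to the training set (70%), validation set (30%), and multiple test sets".

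**The concern.** A model judged on the patients used to fit it looks better than it will in others. Here the reference standard for the comparison (real post-treatment images) is also the material that shaped the generator. Close agreement could therefore reflect learning of those particular patients and not an ability to predict.

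This matters because objective 2 is the only visible place where virtual response is compared directly with real response. The virtual images are then used further on. Section 3 extracts 256-dimensional features from them for survival prediction, and uses simulated differences in tumour regression to compare regimens in the decision support system. An optimistic agreement result would lend those uses support that the data had not provided.

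**Working it through.** The protocol gives no agreement figure, sample size or optimism estimate for this comparison, so there is nothing to reproduce. The check of the concern is textual. The arithmetic at the end describes only the cost of the remedy.

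**1. Which cohort is named?** Item (2), Selection of research subjects, distinguishes four types: retrospective training, retrospective validation, retrospective testing and prospective testing. Objective 2 names one of the four, the training cohort.

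**2. What is that cohort used for?** Section 3 gives the generator real post-treatment images and optimises it against real follow-up images. On the ordinary meaning of a training cohort, these are the same patients and the same images as the comparator in objective 2.

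**3. What is then estimated?** Write A(train) for agreement in the fitting patients and A(new) for agreement in patients the model has not seen. Optimism = A(train) − A(new), which is expected to be positive. The aim in section 2 concerns A(new). Objective 2 as written reports A(train).

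**4. Does other text supply A(new)?**

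| Place in the protocol | What it covers | Supplies held-out response agreement? |
|---|---|---|
| Section 3, model validation strategy | A general split; does not name the ORR/DCR comparison or change its cohort | No |
| Section 3, survival prediction assessment | C-index, time-dependent AUC, Brier score, calibration | No, survival only |
| Section 3, comparative experiment | Clinical model, with real follow-up images, with virtual images | No, listed under survival prediction |
| Section 3, FID below 25 and blinded scores from 3 experts | Visual fidelity and clinical plausibility; no cohort named | No |
| Item (6), ORR and DCR definitions | RECIST 1.1 formulas; no cohort and no virtual-image comparison | No |

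**5. Does the bootstrap repair it?** Item (6), Key research indicators, has "all indicators reported point estimates and 95% confidence intervals (1000 times repeated sampling by the Bootstrap method", and section 3 repeats 1000 resamples for the 95% interval. Resampling the outputs of a fixed model in its own training patients gives an interval around A(train). It would address optimism only if the model were refitted in each resample, which is not stated.

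**6. Cost of moving to test cohorts.** Test-set sizes and agreement rates are not in the protocol; the values here are assumptions.

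- Split: 70% + 30% = 100%, so the source and size of the test sets are not stated.
- 95% half-width = 1.96 × √(p(1 − p)/n), in percentage points:

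| Assumed agreement p | n = 50 | n = 100 | n = 200 |
|---|---|---|---|
| 0.65 | 13.2 | 9.3 | 6.6 |
| 0.75 | 12.0 | 8.5 | 6.0 |
| 0.85 | 9.9 | 7.0 | 4.9 |

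- Interval width relative to the training cohort, at equal agreement, is √(1/r), where r is the ratio of test to training size: r = 0.5 gives 1.41, r = 0.3 gives 1.83, r = 0.1 gives 3.16.
- Time for prospective patients, assuming they start no earlier than 1 June 2025 (the project start in section 6): about 7 months to the end of data collection on 31 December 2025, and about 13 months to the end of model evaluation on 30 June 2026. Section 5 gives a case window that closes in June 2025, so the start date of the prospective cohort itself needs clarifying.

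**The case against.** The strongest reply is that objective 2 does not say the comparison is made only in the training cohort. The English is loose, and the term may mean the development data in general. The validation strategy in section 3 is general and could be meant to cover the generator as well. The SAP was not available, nor was the text between the objectives and item (2), and either might contain a held-out comparison. The comparison of survival models with real and with virtual images also bears on the study's aim. Finally, the generator is optimised on visual features and not on RECIST category, so how much optimism carries over to ORR and DCR agreement is unknown.

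Part of this stands. The criticism is confined to objective 2; survival prediction has validation and test sets. The size of the bias is unknown, for the reason just given among others. A fit check in the training cohort is also legitimate if it is labelled as one.

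The rest does not remove the problem. Item (2) uses training, validation and testing as separate terms, so the plain reading is the natural one. The protocol does not leave the cohort open for the SAP to settle. It names one in a main objective, and text elsewhere that used held-out patients would sit beside that wording without correcting it. If the wording is merely loose, correcting it costs almost nothing.

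**Conclusion.** The concern holds. As written, main objective 2 yields apparent performance for the response comparison and cannot support the claim of prediction from pre-treatment images alone. The expected direction of bias is upward. No size is offered, because the protocol gives no sample size, generator capacity, stopping rule or agreement rate. The conclusion rests on one reading: that the training cohort in objective 2 is the set of patients used to fit the generator. Because this is a main objective and the only visible direct test of virtual against real response, it must be corrected before model evaluation, which section 6 schedules as "2026/01-2026/06: Complete the construction of the generative model, and evaluate and predict the performance of the model".

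**What to change.** - **Research Objectives, main objective 2.** Replace the reference to the training cohort with: *in the held-out retrospective and prospective test cohorts (patients not used to fit or tune the generator), with the model locked and real post-treatment images withheld from it*.
- **Unit of comparison.** Compare virtual and real response category patient by patient. Similar overall ORR or DCR can hide disagreement in individuals.
- **Training-cohort results.** If reported, label them as apparent performance only.
- **Section 3, model validation strategy.** State that the test sets lie outside the 70%/30% training and validation split, and where they come from.

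**Cost.** The change is to wording, with the same analysis run on cohorts already named. The origin of the test sets must be settled first. Reported agreement will probably be lower. Under the assumptions above, intervals would be about 1.4 to 3.2 times as wide as in the training cohort, with half-widths of about 10–13 points for 50 test patients, 7–9 for 100 and 5–7 for 200. The prospective part must wait for best-response imaging; the retrospective test set can be reported first.
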